6 STUDY OBJECTIVES AND PURPOSE

6.1 Primary Objective:

To determine whether dexamethasone decreases the duration of signs and symptoms of ACS. The duration of ACS will be assessed by ACS Assessment (Appendix 3) that incorporate the resolution of tachypnea, hypoxemia, increased work of breathing, and thoracic pain as well as the cessation of medical interventions to support respiration. We predict that dexamethasone will decrease the time to pulmonary recovery.

6.2 Secondary Objectives:

To determine whether dexamethasone reduces morbidity associated with ACS. We predict that dexamethasone will decrease subjects' pain, the requirement for opioid analgesics, the number of transfusions, the use of supplemental oxygen, the duration of hypoxemia, the duration of hospitalization, and the duration of fever.

To determine whether a tapered regimen of dexamethasone prevents rebound VOC. We will study whether a tapered regimen of oral dexamethasone prevents the recurrence of ACS or the development of other VOC soon after ACS. Abrupt discontinuation of a short course of IV corticosteroid may precipitate an early relapse of VOC. As such, we wish to determine whether a longer, tapered course of oral dexamethasone can prevent the relapse of ACS or VOC and readmission to the hospital. We will also document any treatment-related toxicities.

To determine whether dexamethasone modulates the endothelial phenotype to a less proadhesive and procoagulant state, and to determine whether the discontinuation of dexamethasone will be associated with a rebound in the expression of endothelial activation markers of adhesion and coagulation. We predict that the dexamethasone-treated group will demonstrate a decrease (compared to admission values) in plasma levels of VCAM₁, ICAM₁, P-selectin, whole blood tissue factor (WBTF), tissue factor- (TF-) and VCAM₁-positive endothelial microparticles, and ultra-large vWF multimers (vWF/ULVF) at the 48 hour and discharge blood samplings. Inter-group comparisons (placebo vs dexamethasone) will also demonstrate a decrease following dexamethasone when compared to placebo-treated controls. We also predict that the dexamethasone-treated subject group may demonstrate a rebound in plasma levels of VCAM₁, ICAM₁, P-selectin, vWF, WBTF, and TF and VCAM₁-positive endothelial microparticles concomitant with steroid discontinuation.

To determine whether dexamethasone prevents subacute adverse effects of ACS on pulmonary function. Recurrent ACS may cause pulmonary injury and contribute to the development of chronic restrictive lung disease. Decreasing the severity of ACS with dexamethasone might also decrease the severity of late sequelae. We predict that subjects treated with dexamethasone will have better measurements of pulmonary function and more rapid resolution of radiographic pulmonary disease than those treated with placebo.

To determine whether dexamethasone modulates white cell activation and whether the discontinuation of dexamethasone will be associated with a rebound in white cell activation. We predict that plasma L-selectin levels, and monocyte-derived circulating

TF-positive microparticles will decrease during dexamethasone treatment and possibly rebound following steroid discontinuation.

7 STUDY DESIGN

7.1 Description of Study Design

7.1.1 Description Of Primary And Secondary Endpoints

The *primary endpoint* is the duration of signs and symptoms of ACS or the duration of hospitalization, whichever is less. The duration of signs and symptoms of ACS is defined as the interval between first dose of study drug and the time at which the elements of the ACS assessment are satisfied. The ACS assessment incorporate assessments of tachypnea, hypoxemia, work of breathing, thoracic pain, and medical interventions to support respiration (Appendix3). The elements of the ACS assessment will be formally assessed and recorded every 4 hours until discharge from the hospital.

The *secondary endpoints* include the following:

- Amount and type of opioid used;
- Number and type (simple or exchange) of transfusions received;
- Duration of Supplemental oxygen;
- Duration of hospitalization;
- Duration of fever;
- Duration of hypoxemia;
- Rebound hospitalizations;
- Results of pulmonary function testing (FVC, FEV₁, FEF_{25-75%}, PEFR, and flow-volume loop);
- Pulmonary radiographic findings (resolved, improved, unchanged, and worse); and,

- Rating of pain [Oucher or numeric rating scale (both are 0-10 scales)].

The *safety endpoints* include the following:

- Vital signs, including blood pressure;
- Physical examination;
- Urine output and daily fluid balance;
- Blood culture (for fever);
- CBC;
- Reticulocyte count;
- Peripheral oxygen saturation by pulse oximetry;
- AE monitoring;
- Baseline history and interim history (including pain history, pain treatment, respiratory symptoms, inpatient or outpatient evaluations, and management of SCD-related complications); and,
- Concomitant medications monitoring.

The *laboratory endpoints* include the following:

- Plasma soluble biomarkers (VCAM-1, ICAM-1, P-selectin, L-selectin and vWF multimers);
- Flow Cytometry for endothelial microparticles (VCAM₁ and TF) and monocyte microparticles (TF);
- Nitric Oxide metabolites;
- Whole blood tissue factor (WBTF)
- SPLA₂

7.1.2 Description of Type of Study

This is a multi-center, randomized, double-blind, placebo-controlled Phase III clinical trial that will include at least 56 subjects with SCD who are hospitalized for ACS. Individuals who meet entry criteria will be randomized to receive either dexamethasone or placebo. Dexamethasone will be administered initially as 0.3 mg/kg by mouth every 12 hours for a maximum of 4 doses (2 days) or until discharge from the hospital, whichever occurs first. Afterward, the study drug will be tapered over 6 days for a total duration of therapy not to exceed 8 days. Due to possible age-related and ACS severity-related differences in the duration of signs and symptoms of ACS, randomization will be stratified by age and severity of ACS (see Section 8.3). We are enrolling a maximum of 112 pediatric subjects. We will enroll adult subjects at the rate site participation will allow, which we anticipate will be no more than 56 subjects. Interim analyses will be performed when a total of 56 subjects and 112 subjects have completed their hospital stay. If we do not stop enrollment after these interim analyses are completed, we will continue to enroll up to a maximum total of 112 pediatric subjects. The efficacy and safety of dexamethasone will be compared to placebo in the context of standard supportive care for ACS.

8 SELECTION AND WITHDRAWAL OF SUBJECTS

Subjects will be enrolled by study personnel or the physicians who care for them in the emergency department or the inpatient ward after providing informed consent for participation in the study. **Enrollment and Randomization must occur within 24 hours of the diagnosis of ACS, which is timed from the diagnostic chest radiograph. Enrollment is defined as the date and time of signing the informed consent form.**

8.1 Inclusion Criteria

Subjects who meet all of the following criteria are eligible for enrollment into the study:

1. Age \geq 5 years;
2. Diagnosis of sickle cell anemia (Hgb SS) or sickle- β^0 -thalassemia (Hgb S β^0);

3. Current episode of ACS defined as a new lobar or segmental pulmonary infiltrate seen on a chest radiograph and two or more of the following findings in the 24 hours preceding enrollment (signing consent):
 - temperature $\geq 38.5^{\circ}\text{C}$,
 - tachypnea,
 - dyspnea or increased work of breathing,
 - chest wall pain, and
 - oxygen saturation of $< 90\%$ in room air by pulse oximetry;
4. Subjects must have one or more of the following findings at the time enrollment:
 - tachypnea,
 - dyspnea or increased work of breathing,
 - chest wall pain, and
 - oxygen saturation of $< 90\%$ in room air by pulse oximetry;
5. Current episode of ACS diagnosed within the preceding 24 hours;
6. Ability to take medication in capsule form;
7. Written, informed consent provided by the subject and/or parent(s) or guardian(s) before study entry.

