Respiratory therapy: Supplemental oxygen will be administered to maintain a peripheral oxygen saturation of at least 90% by pulse oximetry. Oxygen will be discontinued when the subject maintains a peripheral oxygen saturation of at least 92%, or a documented baseline value, in room air. Arterial blood gas measurements may be performed at the discretion of the attending physician. All subjects should perform incentive spirometry with 10 breaths every two hours from 8 am to 10 pm and every two hours while awake at night.⁷⁷ Young children who are unable to perform incentive spirometry will perform a similar age-appropriate activity, such as blowing bubbles. Chest physiotherapy (CPT) may be prescribed at the discretion of the attending physician. Nebulized bronchodilators may be prescribed at the discretion of the attending physician, and they should be strongly considered for subjects with wheezing or clinical evidence of lower airway obstruction.

Gastrointestinal prophylaxis: All subjects should receive empiric prophylactic treatment with an H₂- (histamine₂-) receptor antagonist, such as ranitidine (2-4 mg/kg/day divided BID with a maximum daily dose of 300 mg), for at least the 8 days of study drug treatment. A different H₂-receptor antagonist or a proton pump inhibitor may be used instead of ranitidine at the treating physician's discretion.

Analgesia: Subjects who are in pain will be treated with ibuprofen (10 mg/kg/dose [maximum 600 mg] p.o. every 6h) and if needed acetaminophen/codeine (1 mg/kg/dose of codeine p.o. every 4-6h). The ibuprofen and acetaminophen/codeine may be alternated every 2 hours. If pain is severe, or oral analgesia is not sufficient, morphine (0.1 mg/kg/dose IV every 2h prn) can be given. The use of continuous infusion morphine or other parenteral opioid analgesics requires caution. Dosing and selection of analgesics can be modified at the discretion of the treating physician to safely achieve optimal pain control.

Transfusion: Attending physicians may prescribe transfusion outside of these guidelines if deemed clinically appropriate. All transfused packed red blood cells (PRBCs) will have extended antigen matching for C, D, E, and Kell, except in the case of emergency.

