10.3 Evaluations by Study Visit

10.3.1 Baseline Evaluations

A chest radiograph is necessary for the diagnosis of ACS, the medical care of the subject, and study enrollment. Immediately after enrolling a subject, the elements of the ACS assessment will be assessed and the following additional assessments performed or measurements taken: history (which includes the collection of any transfusions within 24 hours of enrollment), physical exam, vitals signs (includes blood pressure monitoring), a CBC, blood culture (for those subjects with fever), a pregnancy test if applicable, pain intensity (by Oucher or numeric rating scale), and peripheral oxygen saturation (by pulse oximetry) [See Table 10.2.] Additionally, a blood sample will be drawn for the central laboratory measurements (see Table 10.1).

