13.2.2 Efficacy Analyses

All efficacy analyses will be performed on the ITT population while the primary and some secondary analyses will be repeated on the per-protocol population. Center will be included in the models as permitted by sample size. Center will be eliminated from the models if it appears to be an insignificant variable in the model.

The primary analysis will compare the duration of ACS signs and symptoms (as assessed by the ACS assessment, Appendix3) or the duration of hospitalization for ACS, whichever happens first, of subjects in the dexamethasone treated arm to those in the placebo treated arm. The symptom/hospitalization duration for subjects with ACS will be summarized by treatment group, severity strata, and age strata. The effect of treatment on symptom/hospitalization duration will be tested using a Generalized Linear Mixed Model (GLMM) with the natural log of symptom/hospitalization duration as the outcome variable. The SAS[®] procedure MIXED will be used to fit the GLMM. The GLMM will include treatment, age group, and severity as fixed effects. The GLMM will not specify any variables as random effects or repeated effects, but it will use the GROUP option in the REPEATED statement to estimate separate error variances for each treatment (i.e., GROUP = “treatment”). The SAS[®] procedure MIXED will be used to fit the GLMM.

The GLMM model specified above is necessary for the primary analysis because pilot data give evidence that the length of stay (LOS) in the hospital (which is assumed to be similar to duration of symptoms) for ACS has a lognormal distribution. If the LOS for ACS is distributed as lognormal in each treatment group, then the model of the natural log of LOS must allow for differences in treatment group variances as well as for treatment group mean differences. By allowing for differences in treatment group variances and treatment group means, the treatment group specific distributions can be correctly estimated under the lognormal assumption, resulting in a correct comparison of treatment group means.

As a secondary analysis, parametric survival analysis techniques will be used to estimate distributional parameters and model the hazard function of symptom duration/LOS/hypoxemia/fever for each treatment group. The time to the event of interest (e.g., symptom duration) will be described using a Kaplan-Meier plot stratified by treatment.

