1. The ACS Assessments are completed every 4 hours during hospitalization and at hospital discharge. The first 24 hour period begins at the time of the first dose of study drug on Day 0. i.e. First dose of study drug given on 05JAN07 @ 08:00, therefore Day 0 is from 05JAN07 08:00 – 06JAN07 07:59. The first Q 4 Hour ACS assessment begins as close as possible to 4 hours after first dose of study drug and the next routine nursing assessment. i.e. First dose given at 08:00, next routine nursing assessment is 13:00, therefore begin Q 4 Hour ACS assessments at 13:00 and time the following assessments from this time point. Even if an assessment is missed, this form should be completed and the appropriate expected time point should be selected.
2. Complete in the order the assessments are listed on the ACS Assessment worksheet.
3. Rate the respiratory rate and work of breathing **BEFORE** taking the oxygen off for one minute to check the O₂ saturation.
4. If subject is ventilated or if it is deemed unsafe to trial subject off O₂, then record “NA” (not applicable).
5. If steady state value is not known, enter 92%.
6. Enter a separate pain score for Thoracic and Non-thoracic pain with either the 10 point NRS or the Oucher (subjects 5 – 10 years).
7. **Invasive** ventilatory support means the use of an artificial airway (tracheal intubation) to support breathing. **Noninvasive** support means the use of positive pressure ventilation *without* the need for an invasive artificial airway, e.g. CPAP or BiPAP. The use of incentive spirometry or IPPV alone is **NOT** a form of noninvasive support.

Acute Chest Syndrome Assessment

Date of Assessment: _____

Time of Assessment: _____

Element of Index	Endpoint Criteria	Endpoint Met (Y/N)
1. Respiratory rate		
a. Current rate: _____	$a \leq b$	
b. Upper limit of normal ¹ (bpm) plus 2: _____		
2. Work of breathing		
a. Retractions (Y/N) _____	a = No	
b. Nasal flaring (Y/N) _____	b = No	
c. Use of accessory muscles (Y/N) _____	c = No	
3. Pain		
a. Thoracic pain scale ⁴ _____	$a \leq 4$	
b. Non-Thoracic pain scale _____		
4. S_pO₂ in room air²		
a. Current value: _____	$a \geq b$	
b. Steady-state value ³ (%) minus 2: _____		
5. Medical intervention		
a. Supplemental O ₂ (Y/N) _____	a = No	
b. Invasive or noninvasive ventilatory support (Y/N) _____	b = No	

¹Age 5-11.99 y, 30 bpm; age 12-17.99 y, 25 bpm; age ≥18 y, 20 bpm.

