²If subject is ventilated or if it is deemed unsafe to trial subject off O₂, then record “No” for endpoint met.

³If steady-state value is not known, enter 92% and do not subtract 2.

⁴Enter value of a 0-10 point NRS or Oucher pain scales or the value of a 0-5 point scale multiplied by two.

The study endpoint is met when the answer to each element is “Yes” OR when the subject is discharged (whichever occurs first).

22 APPENDIX 4

Secretory Phospholipase A₂ Assays (Laboratory of [name])

Subject samples will be identified by their unique CSCC subject identifier, specimen number, and date of specimen collection. Subject names will not be used.

Secretory Phospholipase A₂ Assays include:

1). Measurements Secretory Phospholipase A₂ activity will be measured in a fluorescent assay described previously¹. All general calibration and maintenance of the fluorometer will be kept current. Samples will be batched and with appropriate negative and positive controls will consistently be maintained within 10% of the expected values.

2). Measurements Secretory Phospholipase A₂ concentration will be measured using commercially available ELISA Kits (Cayman Chemical, Ann Arbor, MI), which is 100% specific for type IIA sPLA₂. The intra and interassay CV is $\leq 10\%$. General quality control measures will include pipette calibrations to meet standard laboratory guidelines. Samples will be batched and run, with appropriate standard curves performed on the day of sample measurement ($r \geq 0.99$).

Blood Sample Preparation Requirements (total of 8.5ml per blood draw)

TUBE D: **1.0ml** from a free-flowing blood draw will be transferred into a **red-top tube** with no anticoagulant. After 30 minutes at room temperature centrifuge at 2500g for 15 minutes, place supernatant in a thick-walled plastic microfuge tube and freeze at -70°C . Study personnel will batch and send on dry ice every two weeks to [name] Laboratory. [name] laboratory will batch and send every month on dry ice to Red Cell Biology Laboratory.

**Address for Overnight FedEx Shipment to Biomarker Laboratory:
(Monday thru Thursday Shipments Only)**

[name]
Department of Pediatrics
Thomas Jefferson University
[name]
[name]
[name]
[contact]
[contact]

**Address for Overnight FedEx Shipment to Red Cell Biology Laboratory:
(Monday thru Thursday Shipments Only)**

[name]
Department of Red Cell Biology
Children's Hospital Oakland Research Institute

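### Inclusion criterion 4 and the Appendix 3 endpoint use different thresholds, so a subject can be randomized with the primary endpoint already met

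*Protocol*

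**What the plan says.** **Entry.** Protocol Section 8.1, criterion 3 asks for a new infiltrate and two findings in the 24 hours before consent; fever can be one of them. Criterion 4 then says "Subjects must have one or more of the following findings at the time enrollment". Its list repeats that of criterion 3 without temperature: tachypnea, dyspnea or increased work of breathing, chest wall pain, saturation below 90% on room air. Only saturation carries a number.

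**Endpoint.** Appendix 3 has five elements:
- respiratory rate no higher than the age limit (30, 25 or 20 per minute) plus 2;
- no retractions, nasal flaring or accessory-muscle use;
- the item "Thoracic pain scale" at 4 or below;
- room-air saturation at or above the steady-state value minus 2;
- no supplemental oxygen or ventilatory support.

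"The study endpoint is met when the answer to each element is" Yes, or at discharge if that comes first. One all-Yes assessment is enough.

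**Baseline check.** Section 10.3.1: "Immediately after enrolling a subject, the elements of the ACS assessment will be assessed". Its result is not a condition of entry or randomization.

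**Clock and scale.** Section 7.1.1: "The duration of signs and symptoms of ACS is defined as the interval between first dose of study drug and the time" the Appendix 3 elements are satisfied. Appendix 3: "The first Q 4 Hour ACS assessment begins as close as possible to 4 hours after first dose of study drug"; its own example gives 5 h. Section 13.2.2 fits the primary model "with the natural log of symptom/hospitalization duration as the outcome variable".

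**The concern.** Criterion 4 appears meant to ensure that every subject still has active disease at entry: it drops fever, the one criterion 3 finding outside the endpoint domains. The domains line up but the thresholds do not. A subject who passes criterion 4 may have nothing left to resolve on the Appendix 3 scale.

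Such a subject adds no information on the treatment effect. The larger harm comes from the log scale. A duration near 4 h sits far below planning means that correspond to several days, so a few of these subjects in both arms inflate both variances and put a spike at the first assessment. Section 13.3.5 says that the validity of the primary analysis depends on the assumed distribution.

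**Working it through.** **1. Thresholds side by side (subject on room air, other elements met)**

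| Only finding at enrollment | Criterion 4 | Appendix 3 element |
|---|---|---|
| Chest wall pain 1-4 of 10 | met (no score set) | Yes (4 or less) |
| Dyspnea without retractions, flaring or accessory-muscle use | met | Yes (dyspnea is not an element) |
| Rate 1-2 above the age limit (31-32 at 5-11 y, 26-27 at 12-17 y, 21-22 in adults) | met, if tachypnea means above the Appendix 3 limits | Yes (limit plus 2) |

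Example: a new infiltrate, a temperature of 38.5 °C or more in the past 24 h and chest pain of 3/10 satisfy criteria 3 and 4, and all five elements can be Yes before dosing.

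**2. The protocol's sample size (Section 13.4)**

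Inputs: log means 4.25 (placebo) and 3.95 (dexamethasone), log SDs 0.6 and 0.3, two-sided alpha 0.05, Satterthwaite t-test.

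- Noncentrality = 0.30 / √((0.6² + 0.3²)/n).
- n = 54: 0.30 / √(0.45/54) = 3.29, power 0.901. n = 53 gives 0.895, so the stated 54 is reproduced.
- n = 56: 0.30 / √(0.45/56) = 3.35, power 0.911.

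**3. Position of an early score**

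ln 4 = 1.386. Distance from the planning means: (4.25 − 1.386)/0.6 = 4.8 SD for placebo and (3.95 − 1.386)/0.3 = 8.5 SD for dexamethasone.

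**4. Power with a share p of each arm scored at time f**

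With L = ln f, the mean difference is (1−p) × 0.30, and each arm's variance is (1−p)σ² + p(1−p)(μ − L)².

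- p = 2%, f = 4 h: difference 0.294; variances 0.3528 + 0.0196 × 8.20 = 0.514 and 0.0882 + 0.0196 × 6.57 = 0.217 (SDs 0.72 and 0.47); noncentrality 0.294/√(0.731/56) = 2.57; power 0.72.
- p = 5%, f = 4 h: difference 0.285; variances 0.732 and 0.398 (SDs 0.86 and 0.63); noncentrality 0.285/√(1.129/56) = 2.01; power 0.51.

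Simulation with 20,000 trials per setting, 56 per arm, alpha 0.05:

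| First all-Yes | 0% | 1% | 2% | 5% |
|---|---|---|---|---|
| 4 h | 0.91 | 0.81 | 0.73 | 0.52 |
| 5 h | 0.91 | 0.83 | 0.75 | 0.56 |
| 8 h | 0.91 | 0.85 | 0.80 | 0.65 |
| 12 h | 0.91 | 0.88 | 0.84 | 0.73 |

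Of 112 subjects, 1%, 2% and 5% are about 1, 2 and 6. Losing the effect in 5% of subjects with the SDs unchanged would leave 0.88, so the outliers cause most of the loss.

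**5. Other settings the protocol allows (4 h floor)**

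- Log means 4.3 and 3.9, SDs 0.6 and 0.5, within the alternatives accepted in Section 13.4 (mean difference 32 h), 56 per arm, alpha 0.05: 0.97 with none, 0.86 at 2%, 0.70 at 5%.
- Maximum enrollment in Section 7.1.2, 112 children plus 56 adults = 168, or 84 per arm, original planning values, final alpha 0.039: 0.98 with none, about 0.85 at 2%, about 0.64 at 5% (0.86 and 0.65 by the formula).

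**The case against.** **Low saturation as a further route.** A reader might infer that a subject at 89% with a steady state of 91% also enters with the endpoint met. The documents do not support this. Section 9.1.5 says "Supplemental oxygen will be administered to maintain a peripheral oxygen saturation of at least 90% by pulse oximetry", so that subject should be on oxygen, and the medical-intervention element is then No.

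**Zero durations.** A reader might also infer that these subjects have a duration of zero and an undefined logarithm. Under Section 7.1.1 the clock starts at the first dose and the first scheduled assessment is about 4 h later, so the value is small but positive. The Synopsis starts the clock at study entry, which is a separate inconsistency.

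**Tachypnea.** If it is read with the age limits printed in Appendix 3, the gap is only 2 breaths per minute. That is fair; the pain and dyspnea gaps do not depend on it.

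**Size.** It would be too strong to say that power is destroyed. No section gives the share already at endpoint. Subjects are hospitalized with a new infiltrate and must pass all five elements together, and signs may fluctuate, so not all would pass again at the first post-dose check. The 8.5 SD figure also depends on the smallest dexamethasone SD considered. All of this stands and is why a range is shown.

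**Broad entry and later handling.** Section 5 intends to study ACS of any severity, and a statistical analysis plan could say how such subjects are scored. But mild disease is not the same as an endpoint already met, and an analysis plan cannot change who was randomized. All randomized subjects enter the ITT population (Section 13.1).

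**Conclusion.** The mismatch is explicit. On room air, chest pain of 1-4, dyspnea without visible effort or a rate 1-2 above the limit can qualify a subject who already meets the primary endpoint, and the baseline assessment does not stop randomization.

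The size is conditional. A share of 1% to 5% costs about 10 to 39 points of power under the main planning values with a 4 h floor, and about 4 to 18 points with a 12 h floor; the loss is also smaller in the other settings in step 5. These figures assume the same share in both arms and a Welch test in place of the mixed model, without the age and severity covariates. The shares are assumptions, not estimates from the protocol.

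This should be fixed: the correction is cheap and can only act before randomization. The evidence does not show that the trial fails without it.

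**What to change.** Complete the baseline ACS Assessment before randomization, and add to criterion 4 in Section 8.1 that at least one Appendix 3 element is No at that assessment. State the order in Section 10.3.1 as well.

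The cost is one added condition, a fixed order for an assessment already scheduled, and a few subjects with resolved signs who are not randomized.

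The change removes subjects already at endpoint when assessed. It does not remove genuine early responders: a subject with pain 5 at baseline and 4 at the first check still scores about 4 h, because one all-Yes assessment suffices. A full return to 0.91 is therefore not guaranteed.
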